10. IMAGE AND DATA ANALYSIS

10.1. Primary objective

The primary objective is to determine technical feasibility of PET/MRI for rectal cancer treatment response assessment and post-treatment surveillance for patients receiving chemoradiation as part of a NOM strategy. Technical feasibility (**the primary endpoint**) will be defined as completion of the PET/MRI rectal cancer protocol with acceptable image quality in $\geq 70\%$ of scans. This proportion is based on a predicted success rate, informed by prior experience with PET/MRI studies. For patients imaged at multiple time points after enrollment (see 7), all available PET/MRIs will be included in the feasibility analysis. Patients able to remain on the scanner for the full duration of the planned data acquisition without any serious adverse events (see 8.1.2) will be considered to have *completed* the PET/MRI rectal cancer protocol. Image quality will be assessed by the Principal Investigator on review at a dedicated workstation with specialized PET/MR software. A standardized Likert-based scoring scheme will be

utilized to capture subjective assessments of image contrast (1 = worst; 5 = best), image resolution (1 = worst; 5 = best), and image artifact ‘freeness’ (1 = worst; 5 = best). Image sets scoring ≥ 3 in all three categories will be considered of *acceptable quality*.

The first imaging session for the first two subjects enrolled will occur with the Principal Investigator present in the scanner control room to direct the tweaking of acquisition parameters and imaging planes in real time. If the Principal Investigator is satisfied with the quality of the reconstructed PET and MR images from these first two cases, as viewed on a dedicated workstation with specialized PET/MR software, the imaging protocol will be considered optimized, and the relevant acquisition parameters will be ‘locked’ as the default for subsequent imaging sessions for these two patients and for all other enrolled subjects. The Principal Investigator will review each of the remaining cases after it is finished (i.e., not in real time but soon after completion) to simulate conditions under which PET/MRI examinations are typically performed (i.e., technologist operating scanner without radiologist present), making an assessment of image quality at that time according to a predetermined qualitative scale.

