10.2. Secondary objective

The secondary objective is to estimate the added value of PET/MRI relative to MRI only for detecting residual or recurrent rectal cancer following chemoradiation in patients on a NOM protocol. The MRI component of the PET/MRI will be performed as a standard-of-care examination, with the formal study interpretation flowing to the subject’s medical record and replacing the interpretation that would normally be provided by the clinical reading room. These interpretations will include descriptions of local tumor extension (T-stage) and locoregional lymph node involvement (N-stage). Any potential sites of metastatic disease (M-stage) will also be described, though assessment will be limited to the pelvis. For post-treatment imaging studies, an mrTRG will also be provided according to a standardized scale.

Then, the same study reader interpreting the MRI (initially blinded to the PET data) will qualitatively and quantitatively (e.g., post-treatment SUV_{max}) assess the reconstructed PET images (with and without MRI fusion). This reader will then render a PET/MRI tumor regression grade (pmrTRG) based on the PET and MRI data, using a standardized scoring system. Changes in the perceived disease status (i.e., mrTRG vs. pmrTRG; **the secondary endpoint**) will be recorded. This study interpretation will also flow to the patient’s clinical chart via a separate report. The patient’s multidisciplinary care team will consider the pmrTRG in conjunction with results of other available data (e.g., lower endoscopy and DRE) and make a decision whether to categorize the case as cCR.

Subjects deemed to have anything other than cCR will be evaluated for surgical management (TME or endoscopic resection). In contrast, subjects deemed to have a cCR will continue on the NOM surveillance protocol, with repeat PET/MRIs at regular intervals as indicated in the Schema (also see 7). These subsequent PET/MRIs will be analyzed as outlined in the preceding two paragraphs. Thus, the secondary endpoint will consider all scans that each patient undergoes, rather than just the first scan (as outlined in 10.1 for the primary endpoint). Pathology and clinical follow-up

data will be collected for up to 5 years after enrollment of the patient in the study for correlation with the PET/MRI findings.

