11. STATISTICAL CONSIDERATIONS

The primary endpoint is the feasibility of PET/MRI for rectal cancer treatment response assessment and post-treatment surveillance for patients receiving chemoradiation as part of an NOM strategy. We are interested in the feasibility of PET/MRI for this indication to aid in the planning of a larger prospective trial of short-course radiation therapy followed by adjuvant chemotherapy for the NOM of rectal cancer patients, potentially using PET/MRI to assess for residual or recurrent disease following chemoradiation.

The primary endpoint, feasibility, will be analyzed using descriptive statistics, including exact 95% confidence intervals. Similarly, the secondary endpoint, changes in perceived disease status resulting from the addition to FDG-PET to MRI, will also be analyzed with descriptive statistics, including exact 95% confidence intervals.

A sample size of 20 patients, with an anticipated average of 3 scans/patient, will provide approximately 60 scans for feasibility assessment. If we observe a feasibility rate of 83.3% (i.e., 50 of 60 scans completed imaging sessions with adequate image quality), the exact 95% confidence interval for that proportion and sample size would be 72-92%. The lower limit of this confidence interval will effectively indicate that feasibility is $\geq 70\%$ and that the study has met its primary endpoint.

If a feasibility rate of 90% is observed for the first 20 scans after the optimization phase, the 95% confidence interval for that rate would be 68.3-98.8%. This lower bound will be deemed close enough to 70% to constitute success with respect to achieving the primary endpoint. Thus, enrollment of additional subjects could cease at this point (**early stopping**) at the discretion of the Principal Investigator. Notably, already enrolled subjects would continue receiving additional scans per protocol and will be included in the secondary endpoint analysis.

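### The early look and the final feasibility analysis use different scan sets: two pre-lock sessions tuned by the investigator are left out of the first but counted in the second.

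*Combined protocol and SAP*

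**What the plan says.** Section 10.1 separates two conditions of scanning.

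- **Tuned sessions.** "The first imaging session for the first two subjects enrolled will occur with the Principal Investigator present in the scanner control room", and the purpose is "to direct the tweaking of acquisition parameters and imaging planes in real time". If the investigator is satisfied with the images from these two cases, the parameters become the default for all later sessions.
- **Routine sessions.** The remaining cases are reviewed after the scan is finished, "to simulate conditions under which PET/MRI examinations are typically performed", that is, with a technologist and no radiologist present.

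The plan then describes the scans behind the primary endpoint in different ways.

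- **Final analysis, 10.1:** "all available PET/MRIs will be included in the feasibility analysis". No exception is made for the tuned sessions.
- **Final analysis, 11:** "A sample size of 20 patients, with an anticipated average of 3 scans/patient, will provide approximately 60 scans for feasibility assessment". This is 20 × 3 with nothing taken out.
- **Early look, 11:** "If a feasibility rate of 90% is observed for the first 20 scans after the optimization phase", enrollment may stop.
- **Aside in 10.2:** the secondary endpoint uses all scans "rather than just the first scan (as outlined in 10.1 for the primary endpoint").

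The term optimization phase is not defined. From 10.1 it appears to mean the two tuned sessions. The plan does not say what follows if the investigator is not satisfied after two.

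**The concern.** The endpoint is meant to show how often the examination works in ordinary use. By the plan's own account, two sessions are not ordinary: the parameters are still open and an expert is adjusting them during the scan. The same investigator later gives the Likert scores that define acceptable quality. Counting these sessions puts set-up cases among the test cases.

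The early look leaves them out, and no reason is given for treating the final analysis differently. At stake is a denominator that could be settled after the results are known, for an endpoint judged by whether an exact lower limit reaches 70%. Near that limit, two scans can decide the outcome.

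**Working it through.** **Inputs.** 2 tuned sessions (10.1); about 60 scans, the 50/60 example, the early-look example of 90% of 20 scans (18/20), and the 70% threshold (10.1 and 11). Assumptions: the optimization phase is exactly these two sessions, and scans are independent, as the plan's own interval treats them.

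**Step 1. The plan's figures.** Clopper-Pearson 95% limits for x of n: lower = Beta(0.025; x, n−x+1), upper = Beta(0.975; x+1, n−x).

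- 50/60: 71.5-91.7% (plan: 72-92%; the lower limit is 71.48%, which is 71 to a whole percent).
- 18/20: 68.3-98.8%, as stated.

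**Step 2. Shift in the expected rate.** Let p be the routine success rate. If both tuned sessions succeed, the expected 60-scan rate rises by (2/60)(1−p). If both fail, it falls by (2/60)p.

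| p | both succeed | both fail |
|---|---|---|
| 0.70 | +1.0 point | −2.3 points |
| 0.833 | +0.6 | −2.8 |
| 0.90 | +0.3 | −3.0 |

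Under a first-scan-only reading of 10.2 the weight is 2/20, so at p = 0.833 the rise would be at most (2/20)(0.167) = 1.7 points.

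**Step 3. The 60-scan example.** The smallest count with a lower limit of at least 70% is 50 of 60 (49/60 gives 69.6%). If both tuned sessions succeed, 48 of the 58 routine scans must succeed. With the two excluded, the smallest passing count is 48 of 58 (70.6-91.4%; 47/58 gives 68.6%). The requirement is the same, so the chance of passing is the same: P(X ≥ 48 | 58, 0.70) = 2.0%, and 62.9% at a true rate of 50/60.

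**Step 4. Nearby totals.** The plan says approximately 60, so the final count may differ. With N scans in all, both tuned sessions successful, and pass marks found as in step 3:

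| N | routine successes needed, counting them | needed, excluding them | false pass at p = 0.70, counting | excluding |
|---|---|---|---|---|
| 57 | 45 of 55 | 46 of 55 | 3.4% | 1.6% |
| 58 | 46 of 56 | 47 of 56 | 2.9% | 1.3% |
| 59 | 47 of 57 | 47 of 57 | 2.4% | 2.4% |
| 60 | 48 of 58 | 48 of 58 | 2.0% | 2.0% |
| 61 | 48 of 59 | 49 of 59 | 3.5% | 1.7% |

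At 57, 58 and 61, counting two successes lowers the routine requirement by one, and the false-pass chance exceeds the 2.5% nominal for one side of a 95% interval.

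**Step 5. Near an early stop.** 18/20 has a lower limit of 68.3%. Adding two tuned successes gives 20/22 = 90.9%, with limits 70.8-98.9%, which crosses 70%.

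**The case against.** The strongest reply has four parts.

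1. **The inclusion is inferred.** The sentence in 10.1 about including all scans opens with patients imaged at several time points, so it may address repeat scans only, and approximately 60 could also mean 58. This has some force: the plan is silent rather than explicit. But the wording admits no exception, section 11 multiplies 20 by 3, and only the early look carries a restriction. Read as written, the two sessions count.
2. **Upward bias is not shown.** A reader might infer that live tuning makes these sessions near-certain successes. The documents do not support that. Section 10.1 says the parameters are locked if the investigator is satisfied, not that tuning continues until then. Section 7 caps imaging at 60 minutes. Success also requires the patient to complete the acquisition without a serious adverse event. Scans made before the parameters are settled could score worse. This objection stands.
3. **The operating characteristics do not improve at 60 scans.** A reader might compare 50/60 with 48 of the other 58 and conclude that counting the sessions raises the false-pass chance from 1.4% to 2.0%, and the pass chance at 83.3% from 58% to 63%. That comparison fails: the lower figures belong to 60 routine scans, which neither version provides. Step 3 shows that exclusion gives the same 2.0% and 62.9%. This also stands.
4. **The first-scan wording in 10.2 is the larger conflict.** It does contradict 10.1 on its natural reading, although the parenthesis could be meant to refer to all scans. Either way it belongs in the same correction.

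**Conclusion.** The inconsistency is real and minor. As written, the early look and the final analysis use different scan sets, the final set includes two sessions run under non-routine conditions, and 10.2 adds what reads as a third definition.

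The direction of any bias is open: upward is plausible because the tuner also scores, but the documents do not establish it. The case for exclusion does not depend on direction, because these sessions fall outside the conditions the endpoint is meant to describe.

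If both succeed, the rate rises by at most about 1 point over 60 scans for a true rate of 70% or more, and the 60-scan example still passes either way. The choice can matter at particular totals such as 57 or 61, where the false-pass chance roughly doubles, and close to an early stop. These results assume two optimization sessions, both successful, and independent scans; clustering within patients would change the probabilities.

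**What to change.** In 10.1 and 11, define one primary analysis set that excludes the optimization-phase sessions at both the early look and the final analysis. State which sessions form that phase and how its end is determined if two are not enough. Report these sessions separately, with their completion status and scores. Correct the first-scan wording in 10.2 so that it agrees with 10.1. Restate the example on about 58 scans: 48/58 = 82.8%, exact 95% CI 70.6-91.4%.

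The cost is a few sentences, two fewer scans in the denominator, and a slightly lower limit in the example (70.6% instead of 71.5%), still above 70%. The change is best made before any scores are reviewed, so that the choice of denominator cannot appear to depend on the results.

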10.2. Secondary objective

The secondary objective is to estimate the added value of PET/MRI relative to MRI only for detecting residual or recurrent rectal cancer following chemoradiation in patients on a NOM protocol. The MRI component of the PET/MRI will be performed as a standard-of-care examination, with the formal study interpretation flowing to the subject’s medical record and replacing the interpretation that would normally be provided by the clinical reading room. These interpretations will include descriptions of local tumor extension (T-stage) and locoregional lymph node involvement (N-stage). Any potential sites of metastatic disease (M-stage) will also be described, though assessment will be limited to the pelvis. For post-treatment imaging studies, an mrTRG will also be provided according to a standardized scale.

Then, the same study reader interpreting the MRI (initially blinded to the PET data) will qualitatively and quantitatively (e.g., post-treatment SUV_{max}) assess the reconstructed PET images (with and without MRI fusion). This reader will then render a PET/MRI tumor regression grade (pmrTRG) based on the PET and MRI data, using a standardized scoring system. Changes in the perceived disease status (i.e., mrTRG vs. pmrTRG; **the secondary endpoint**) will be recorded. This study interpretation will also flow to the patient’s clinical chart via a separate report. The patient’s multidisciplinary care team will consider the pmrTRG in conjunction with results of other available data (e.g., lower endoscopy and DRE) and make a decision whether to categorize the case as cCR.

Subjects deemed to have anything other than cCR will be evaluated for surgical management (TME or endoscopic resection). In contrast, subjects deemed to have a cCR will continue on the NOM surveillance protocol, with repeat PET/MRIs at regular intervals as indicated in the Schema (also see 7). These subsequent PET/MRIs will be analyzed as outlined in the preceding two paragraphs. Thus, the secondary endpoint will consider all scans that each patient undergoes, rather than just the first scan (as outlined in 10.1 for the primary endpoint). Pathology and clinical follow-up

data will be collected for up to 5 years after enrollment of the patient in the study for correlation with the PET/MRI findings.

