4.2. Secondary objective

To estimate the added value of PET/MRI relative to MRI only for detecting residual or recurrent rectal cancer following chemoradiation in patients on an NOM protocol.

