7. STUDY PROCEDURES

Study subjects will be recruited from the population of adult patients referred to Washington University's Radiation Oncology program for an initial biopsy-proven diagnosis of rectal cancer (Enrollment point #1) or previously treated with chemoradiation by Washington University's Radiation Oncology program as part of a NOM strategy for rectal cancer (Enrollment points #2 and #3). Individuals treated with equivalent regimens at other institutions are not eligible. Note that Enrollment point #3 can include patients that have already undergone one or more standard-of-care surveillance imaging sessions. Furthermore, for subjects entering at Enrollment points #2 and #3, there is no requirement that a subject have undergone an FDG-PET examination previously to be eligible.

Patients who meet the inclusion criteria will be recruited to undergo FDG-PET/MRI in lieu of the standard pelvic MRI at ***up to 6 time-points*** at which it would normally be performed in their care for the period of time extending 30-36 months from the time of enrollment (depending on enrollment point). In the surveillance period, when patients typically undergo pelvic MRI every 3 months, the FDG-PET/MRI will be done in lieu of the standard pelvic MRI on an approximately every-other-scan basis. In other words, the FDG-PET/MRI will occur roughly once every 6 months. Target enrollment is 10 patients by the end of year 1 of recruitment and 20 patients by the end of year 2 of recruitment (unless early stopping rule is

satisfied). For subjects entering study at each of the three time points, imaging will consist of the following, assuming no indication for surgery or exclusion criterion is identified:

1. Enrollment point #1 (6 imaging sessions)
 - a. Initial staging FDG-PET/MRI
 - b. Restaging FDG-PET/MRI
 - c. Surveillance FDG-PET/MRI #1
 - d. Surveillance FDG-PET/MRI #2
 - e. Surveillance FDG-PET/MRI #3
 - f. Surveillance FDG-PET/MRI #4
2. Enrollment point #2 (6 imaging sessions)
 - a. Restaging FDG-PET/MRI
 - b. Surveillance FDG-PET/MRI #1
 - c. Surveillance FDG-PET/MRI #2
 - d. Surveillance FDG-PET/MRI #3
 - e. Surveillance FDG-PET/MRI #4
 - f. Surveillance FDG-PET/MRI #5
3. Enrollment point #3 (6 imaging sessions)
 - a. Surveillance FDG-PET/MRI #1
 - b. Surveillance FDG-PET/MRI #2
 - c. Surveillance FDG-PET/MRI #3
 - d. Surveillance FDG-PET/MRI #4
 - e. Surveillance FDG-PET/MRI #5
 - f. Surveillance FDG-PET/MRI #6

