7.3. Clinical record

We will collect information from the patient's medical record such as standard of care images and other clinical records for up to 5 years following the last imaging examination performed on protocol. The purpose of this follow-up period is to correlate imaging findings with patient outcomes, as many patients will likely not undergo surgery for residual or recurrent disease during the 24-36 month study period.

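### The secondary analysis reports how often adding PET changed the regression grade, not how often the change was right, and its exact interval makes no allowance for repeat scans of a patient

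*Combined protocol and SAP*

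**What the plan says.** Section 4.2 sets the secondary objective: "To estimate the added value of PET/MRI relative to MRI only for detecting residual or recurrent rectal cancer". Section 10.2 has one reader grade the MRI first (mrTRG) and then, with the PET images, give a combined grade (pmrTRG). The secondary endpoint is "Changes in the perceived disease status (i.e., mrTRG vs. pmrTRG". All scans of a patient count towards it, but an mrTRG is given only for post-treatment scans.

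Section 11 says that the secondary endpoint "will also be analyzed with descriptive statistics, including exact 95% confidence intervals". The sentence is framed as parallel to the one on the primary endpoint, whose worked example counts scans: 20 patients, "with an anticipated average of 3 scans/patient, will provide approximately 60 scans for feasibility assessment".

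Outcome data are collected. Section 10.2 says that pathology and clinical "data will be collected for up to 5 years after enrollment of the patient in the study for correlation with the PET/MRI findings". Section 7.3 says "The purpose of this follow-up period is to correlate imaging findings with patient outcomes", and sets the period as "for up to 5 years following the last imaging examination performed on protocol". Section 10.2 also has the care team weigh the pmrTRG when deciding whether a case is a complete clinical response (cCR), and patients without a cCR are evaluated for surgery.

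**The concern.** Added value for detection depends on whether PET moved the grade towards the truth. A change count does not show this: ten justified upgrades and ten false alarms give the same rate. The study exists to inform later trials, and a designer of such a trial would need the share of correct changes in each direction.

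Patients may have up to six scans. Scans of one patient share a tumour and treatment history, and 10.2 has the same reader give both grades of a scan. If a change on one scan makes a change on another scan of that patient more likely, an exact binomial interval over scans claims too much precision.

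**Working it through.** **1. What Section 11 would deliver.** Set beside each other, 4.2 asks about detection, 10.2 records a difference between two grades, and Section 11 gives its frequency with an interval. Direction can be recovered from the paired grades. Correctness cannot be recovered from the grades alone. The documents state no reference standard, no grade that counts as disease, no scan-to-outcome window and no method for the correlation that 7.3 and 10.2 intend.

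**2. The plan's own intervals.** Clopper-Pearson with scans as independent units gives 71.5-91.7% for 50/60 (plan: 72-92%; the lower limit, 71.48%, would round to 71) and 68.3-98.8% for 18/20 (plan: the same). The method is therefore the exact binomial over scans. These are primary-endpoint figures; the secondary endpoint has none of its own.

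**3. Denominator.** 20 patients x 3 scans = 60. Initial staging scans carry no mrTRG. If all 20 patients enter at point #1, 60 - 20 = 40 scans can show a change; if none do, 60. Early stopping would lower both.

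**4. Effect of repeat scans.** The plan gives neither a change rate nor a within-patient correlation (rho), so both are assumed: 20% changed, rho 0.2 or 0.5, and equal numbers of scans (m) per patient. Design effect DE = 1 + (m - 1) x rho; effective n = n / DE; the interval is Clopper-Pearson at the effective n.

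| Scans | rho | DE | Effective n | 95% interval |
|---|---|---|---|---|
| 60 (m = 3), 12 changed | 0 | 1.0 | 60 | 10.8-32.3% |
| | 0.2 | 1.4 | 42.9 | 9.4-35.0% |
| | 0.5 | 2.0 | 30.0 | 7.7-38.6% |
| 40 (m = 2), 8 changed | 0 | 1.0 | 40 | 9.1-35.6% |
| | 0.2 | 1.2 | 33.3 | 8.2-37.4% |
| | 0.5 | 1.5 | 26.7 | 7.1-39.9% |

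In beta-binomial simulation (20 patients, true rate 20%), the unadjusted 95% interval covers about 93% (rho 0.2) and 86% (rho 0.5) with three scans each, and about 96% and 93% with two. At rho 0.1 and three scans it covers about 95%, because the exact method's own conservatism nearly offsets the clustering.

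**5. Which adjustment.** A percentile bootstrap over patients is the usual suggestion, but it does poorly here. At a true rate of 10% with two scans per patient, it covers about 89% and 86% (rho 0.2 and 0.5), against about 95% and 92% for the unadjusted exact interval. With no changes observed it collapses to 0-0. The exact interval at the design-effect-adjusted sample size covered at least as well as both in every case run (about 92-98%).

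**6. Follow-up left after the last scan.** Section 7 schedules imaging "for the period of time extending 30-36 months from the time of enrollment"; 7.3 speaks of a 24-36 month study period. For a last scan at month 24-36, five years from enrollment leaves 60 - 36 = 24 to 60 - 24 = 36 months, while five years from the last scan leaves 60. The gap is 24-36 months. With three scans about six months apart, the first near enrollment, the last is near month 12: 48 against 60 months, a gap of 12.

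**The case against.** This is a 20-patient pilot whose main question is feasibility. A change rate is a legitimate descriptive pilot result, and reporting direction already fits within descriptive statistics. That stands, and the raw rate should be kept. It does not close the gap between the endpoint and the wording of the objective.

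A reader might infer that the plan ignores outcomes, or that the study cannot tell right changes from wrong ones. The documents do not support this. Sections 7.3 and 10.2 both collect outcomes in order to correlate them with imaging, so the data should allow at least some changes to be classified. What is missing is the rule and the analysis.

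A reader might also infer that the secondary interval is stated to be per scan and is materially wrong. Section 11 does not name its unit; per scan is inferred from the all-scans rule in 10.2 and the parallel with the primary endpoint. The shortfall in coverage depends on an unknown correlation and is modest or absent in several plausible cases.

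Finally, the calculations assume equal scans per patient, whereas patients who have surgery for suspected recurrence contribute no later surveillance scans. A per-scan rate therefore leans towards patients who stay in surveillance. That imbalance is not quantified here.

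**Conclusion.** The point holds in two parts of unequal weight. The main one needs no assumption: Section 11 as written gives the frequency of grade changes and does not use the outcome data that would show whether they were right. The second is conditional. If the interval is per scan and scans within a patient are positively correlated, it is too narrow: 10.8-32.3% widens to 9.4-35.0% or 7.7-38.6% for 12/60 at assumed correlations of 0.2 or 0.5, and less with two scans per patient.

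No test or decision rule uses the secondary interval, so no error rate or power figure is at stake, and nothing here changes the definition of the primary endpoint. The two follow-up periods contradict each other and limit how late scans can be verified. The amendment is worth making, but the point does not threaten the study.

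**What to change.** In Section 11:

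1. **Classify the changes.** Before reads, fix the grade on each scale that counts as disease. For post-chemoradiation scans with both grades, report upgrades and downgrades separately, each as correct, incorrect or unclassified. Judge against pathology where available, otherwise against local disease status over a fixed window after that scan. Do not use the cCR label as the reference, because pmrTRG feeds that decision. Label these results exploratory, and state that verification depends partly on pmrTRG.
2. **Adjust the interval.** Keep the raw change rate, with a Clopper-Pearson interval at the effective sample size from the estimated design effect, never narrower than the unadjusted interval. Use this rather than a percentile patient bootstrap. Add per-patient summaries: any change, and the first graded scan. Note that the first graded scan is restaging for enrollment points #1 and #2 but surveillance for point #3.
3. **Reconcile the follow-up periods** in 7.3 and 10.2, so that the fixed window can be met for late scans.

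The cost is SAP wording and modest analysis of data already being collected, with no added scans, patients or readers. The downsides are slightly wider intervals, low precision for the correctness results, and some scans left unclassified.
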